7.2.1. Discontinuation of Inadvertently Enrolled Participants

If the sponsor or investigator identify a participant who did not meet enrollment criteria and was inadvertently enrolled, then the participant should be discontinued from study drug unless there are extenuating circumstances that make it medically necessary for the participant to continue on study drug. If the investigator and the sponsor-designated medical monitor agree it is medically appropriate to continue, the investigator must obtain documented approval from the sponsor-designated medical monitor to allow the inadvertently enrolled participant to continue in the study with or without treatment with the study drug. Safety follow up is as outlined in Section 1.3 (Schedule of Activities), Section 8.2 (Safety Assessments), and Section 8.3 (Adverse Events and Serious Adverse Events) of the protocol.

7.3. Lost to Follow up

A participant will be considered lost to follow-up if he or she repeatedly fails to return for scheduled visits and is unable to be contacted by the study site. Site personnel are expected to make diligent attempts to contact participants who fail to return for a scheduled visit or were otherwise unable to be followed up by the site.

Site personnel, or an independent third party, will attempt to collect the vital status of the participant within legal and ethical boundaries for all participants randomized, including those who did not get the study drug. Public sources may be searched for vital status information. If vital status is determined to be deceased, this will be documented and the participant will not be considered lost to follow-up. Sponsor personnel will not be involved in any attempts to collect vital status information.

8. Study Assessments and Procedures

Study procedures and their timing are summarized in the SoA.

Immediate safety concerns should be discussed with the sponsor immediately upon occurrence or awareness to determine if the participant should continue or discontinue study intervention.

Adherence to the study design requirements, including those specified in the SoA, is essential and required for study conduct.

All screening evaluations must be completed and reviewed to confirm that potential participants meet all eligibility criteria. The investigator will maintain a screening log to record details of all participants screened and to confirm eligibility or record reasons for screening failure, as applicable.

8.1. Efficacy Assessments

8.1.1. Primary Outcome Measures: Vaccine Responses

Seroresponses to vaccines will be assessed as follows:

- Tdap vaccine: a booster response as measured by tetanus toxoid-specific IgG antibodies
- MCV: a positive antibody response to Group C serum bactericidal antibodies

For details about the primary endpoints and definitions of the booster response and positive antibody response, see Section 3.

For details about the laboratory tests to support the primary outcome measure, see Appendix 10.2. For frequency of these tests, see the SoA (Section 1.3).

8.1.2. Secondary Outcome Measures: Efficacy

Each participant's AD will be assessed as specified in the SoA (Section 1.3). Whenever possible, the same assessor should perform all assessments on a given participant over the course of the study. The sponsor will administer training on the required efficacy assessments; detail on the specific instruments and training given are recorded in the study training materials.

All clinician-reported efficacy assessments will be captured on an electronic tablet during the site visits after all the patient-reported outcomes have been completed.

Appropriateness of assessments

All the assessments used in this study are relevant for the AD population. Some measures have been validated and are widely used, including the following:

- EASI (Hanifin et al. 2001)
- POEM (Charman et al. 2004)
- Skin Pain NRS (Newton et al. 2019; data on file)

8.1.2.1. Investigator Global Assessment (IGA)

The IGA is a static assessment and rates the severity of the participant's AD. The IGA is comprised of a 5-point scale ranging from 0 (clear) to 4 (severe), and a score is selected using descriptors that best describe the overall appearance of the lesions at a given time point. It is not necessary that all characteristics under Morphological Description be present.

Assessors must be trained and certified by the sponsor prior to conducting this assessment. The IGA must be conducted prior to conducting the EASI and BSA assessments. A single assessor should be assigned to each individual participant for as many visits as possible, to avoid inter-assessor variability in scoring.

8.1.2.2. Eczema Area and Severity Index (EASI)

The EASI is a validated measure that evaluates 2 dimensions of AD: disease extent and clinical signs (Hanifin et al. 2001).

The EASI assesses extent of disease at 4 body regions and measures 4 clinical signs, each on a scale of 0 to 3:

- (1) erythema
- (2) induration/papulation
- (3) excoriation, and
- (4) lichenification.

The EASI is a composite index with scores ranging from 0 to 72, with the higher values indicating more severe or extensive disease.

Assessors must be trained and certified by the sponsor prior to conducting this assessment.

8.1.2.3. Body Surface Area (BSA)

The BSA assessment estimates the extent of disease or skin involvement with respect to AD and is expressed as a percentage of total body surface. BSA will be determined by the investigator or designee using the participant palm = 1% rule.

Assessors must be trained and certified by the sponsor prior to conducting this assessment.

8.1.3. Patient-Reported Outcomes

The outcome measures used in this study are relevant to the AD population.

Participants will complete these assessments as follows, prior to the other study assessments; see also the SoA (Section 1.3):

- Electronic diary (completed at home):
 - Pruritus NRS (daily)
 - Sleep-Loss (daily)
 - Skin Pain NRS (daily)
 - POEM (weekly)
- Electronic tablet (provided at the site):

- PROMIS® Anxiety
- PROMIS® Depression

8.1.3.1. Pruritus Numeric Rating Scale (NRS)

Participants will assess pruritus using a Pruritus NRS. The Pruritus NRS is an 11-point scale used by patients to rate their worst itch severity over the past 24 hours, with 0 indicating “No itch” and 10 indicating “Worst itch imaginable.”

Participants will record the pruritus assessments daily using an electronic diary at home. As indicated in the SoA (Section 1.3), initial electronic diary entries for Pruritus NRS should be completed a minimum of 4 of 7 days before randomization.

8.1.3.2. Sleep-Loss

Participants will assess their Sleep-Loss due to pruritus. They will rate their sleep based on a 5-point Likert scale: 0 (not at all) to 4 (unable to sleep at all).

Participants will record their Sleep-Loss assessments daily using an electronic diary at home. As indicated in the SoA (Section 1.3), initial electronic diary entries for Sleep-Loss should be completed a minimum of 4 of 7 days before randomization.

8.1.3.3. Skin Pain Numeric Rating Scale (NRS)

Skin Pain NRS (Newton et al. 2019) is a patient-administered, validated, 11-point horizontal scale anchored at 0 and 10, with 0 representing “no pain” and 10 representing “worst pain imaginable.” Overall severity of a patient’s skin pain is indicated by selecting the number that best describes the worst level of skin pain in the past 24 hours.

Participants will record the Skin Pain NRS assessments daily using an electronic diary at home. As indicated in the SoA (Section 1.3), initial electronic diary entries for Skin Pain NRS should be completed a minimum of 4 of 7 days before randomization.

8.1.3.4. Patient-Oriented Eczema Measure (POEM)

The POEM (Charman et al. 2004) is a 7-item, validated questionnaire used by the patient to assess disease symptoms over the last week. The patient is asked to respond to 7 questions on:

- skin dryness
- itching
- flaking
- cracking
- sleep loss
- bleeding, and
- weeping.

All 7 answers carry equal weight with a total possible score from 0 to 28 (answers scored as: No days = 0; 1–2 days = 1; 3–4 days = 2; 5–6 days = 3; everyday = 4). A high score is indicative of a poor quality of life.

Participants will capture the POEM responses weekly using an electronic diary at home.

8.1.3.5. Patient-Reported Outcomes Measurement Information System (PROMIS®): Anxiety and Depression

Patient-Reported Outcomes Measurement Information System is a set of person-centered measures that evaluates and monitors patient's physical, mental, and social health (PROMIS WWW).

The PROMIS® measures used in this study include Anxiety and Depression short forms, which assess the patients' symptoms over the previous week.

Participants will complete the PROMIS measures on an electronic tablet on site (see the SoA for frequency; Section 1.3).

PROMIS® Anxiety

This trial uses the PROMIS Short Form v1.0 – Anxiety -8a. The PROMIS® Anxiety short form assesses the following items (PROMIS Anxiety 2019):

- self-reported fear (fearfulness, panic)
- anxious misery (worry, dread)
- hyperarousal (tension, nervousness, restlessness), and
- somatic symptoms related to arousal (racing heart, dizziness).

Each question has 5 response options, with scores ranging from 1 to 5. The total scores range from 8 to 40, with the higher score indicating a higher level of anxiety.

PROMIS® Depression

This trial uses PROMIS Short Form v1.0 – Depression 8b. The PROMIS® Depression short form assesses the following items (PROMIS Depression 2019):

- self-reported negative mood (sadness, guilt)
- views of self (self-criticism, worthlessness)
- social cognition (loneliness, interpersonal alienation), and
- decreased positive affect and engagement (loss of interest, meaning, and purpose).

Somatic symptoms (such as changes in appetite or sleeping patterns) are not included. This helps eliminate potential confounding effects of these items when assessing participants with comorbid physical conditions.

Each question has 5 response options, with scores ranging from 1 to 5. The total scores range from 8 to 40, with the higher score indicating a higher level of depression.

8.2. Safety Assessments

Planned time points for all safety assessments are provided in the SoA (Section 1.3).

8.2.1. Physical Examinations

A complete physical examination will cover general appearance and the following body parts and systems:

- dermatological
- head
- ears
- eyes
- nose
- throat
- respiratory
- cardiovascular
- abdominal
- neurological
- musculoskeletal, and
- lymphatic.

Height and weight will also be recorded.

At subsequent study visits, a symptom-directed physical examination may be conducted at the discretion of the investigator. Findings will be recorded as medical history or AE in the eCRF.

8.2.2. Vital Signs

Vital signs, including body temperature, respiratory rate (breaths per minute), pulse (beats per minute), and blood pressure (mmHg), will be obtained with the participant in the seated position, after sitting for at least 5 minutes. Any abnormal findings that are new or worsened in severity and clinically significant, in the opinion of the investigator, will be recorded as an AE. Vital sign measurements will be recorded in the eCRF.

8.2.3. Clinical Safety Laboratory Assessments

See Appendix 10.2 for the list of clinical laboratory tests to be performed and to the SoA for the timing and frequency.

Reviewing and recording test results

The investigator must review the laboratory report, document this review, and record any clinically relevant changes occurring during the study in the AE section of the eCRF. The laboratory reports must be filed with the source documents. Clinically significant abnormal laboratory findings are those which are not associated with the underlying disease, unless judged by the investigator to be more severe than expected for the participant's condition.

Repeat testing after clinically significant abnormal findings

All laboratory tests with values considered clinically significantly abnormal during participation in the study or within 28 days after the last dose of study intervention should be repeated until the values return to normal or baseline or are no longer considered clinically significant by the investigator or medical monitor.

- If such values do not return to normal/baseline within a period of time judged reasonable by the investigator, the etiology should be identified and the sponsor notified.
- All protocol-required laboratory assessments, as defined in Appendix [10.2](#), must be conducted in accordance with the laboratory manual and the SoA.

If laboratory values from non-protocol specified laboratory assessments performed at the institution's local laboratory require a change in participant management or are considered clinically significant by the investigator (e.g., SAE or AE or dose modification), then the clinically significant results will be reported as an AE in the AE section of the eCRF.

Blinding of laboratory test results

Laboratory results that could unblind the study will not be reported to investigative sites or other blinded personnel (Appendix [10.2](#)).

8.2.3.1. Pregnancy Testing

Pregnancy testing is to be performed on WOCBP. Participants who are pregnant will be discontinued from the study (Section [7.2](#)).

Visits and times

Serum pregnancy test will be done at screening only, and results will be confirmed by the central laboratory, as stated in Appendix [10.2](#).

Urine pregnancy testing will be performed locally at visits specified in the SoA (Section [1.3](#)). If the specified visit includes study drug administration, the urine pregnancy test must be "negative" within 24 hours before the study drug is administered.

Urine pregnancy testing may be performed at additional time points during the study treatment period and/or follow-up period, at the discretion of the investigator or if this is required by local regulations.

8.2.4. Systemic Hypersensitivity Reactions

Many drugs, but particularly biologic agents, carry the risk of systemic hypersensitivity reactions. Vaccines may be associated with such hypersensitivity reactions, as well. If such a reaction occurs, additional data describing each symptom should be provided to the sponsor in the eCRF.

Sites should have appropriately trained medical staff and appropriate medical equipment available when study participants are receiving the study intervention. It is recommended that

participants who experience a systemic hypersensitivity reaction be treated per national and international guidelines.

In the case of generalized urticaria or anaphylaxis, additional blood and urine samples should be collected as described in Appendix 10.5. Laboratory results are provided to the sponsor via the central laboratory.

8.2.5. Hepatitis B Testing and Monitoring

Initial testing for HBV infection includes (CDC WWW):

- hepatitis B surface antigen (HBsAg)
- hepatitis B core (anti-HBc), and
- hepatitis B surface antibody (anti-HBs).

If ...	Then ...
HBsAg is positive	the participant is excluded.
HBsAg is negative and anti-HBs is positive (regardless of anti-HBc result) OR HBsAg, anti-HBs, and anti-HBc are all negative	the participant is not excluded.
anti-HBc is positive and HBsAg and anti-HBs are negative	
further testing for HBV DNA is required:
 
 • If the screening HBV DNA is positive, the participant is excluded. • If the screening HBV DNA is negative, the participant is not excluded. Repeat testing for HBV DNA is required at least every 3 months during the study (Section 1.3), with temporary withholding or permanent discontinuation of study intervention if HBV DNA is positive, as described in Sections 7.1.1 and 7.1.2, respectively.

Management of enrolled participants with detectable HBV DNA during the study

See Sections 7.1.1 and 7.1.2.

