1.2. Schema

Abbreviations: MCV = Meningococcal (Groups A, C, Y, and W-135) Oligosaccharide Diphtheria CRM197 Conjugate Vaccine (GlaxoSmithKline); Q2W = once every 2 weeks; Tdap = Diphtheria and Tetanus Toxoids and Acellular Pertussis Vaccine Adsorbed (Sanofi).

- ^a Lebrikizumab loading dose of 500 mg will be administered at baseline and Week 2.
- ^b The safety follow-up will occur at Week 26 (or approximately 12 weeks after last study drug injection). See Section 4.4 for completion of study definitions.
- ^c If eligible, participants can continue to the long-term extension study (DRM06-AD07/J2T-DM-KGAA). See Section 4.4 for completion of study definitions.

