1.3. Schedule of Activities (SoA)

The SoA described below should be followed for all participants enrolled in Study KGAK. However, for those participants whose participation in this study is affected by exceptional circumstances (such as pandemics or natural disasters), please refer to Appendix 10.9 for additional guidance.

Notes:												

 Visit 1 procedures may be conducted over more than 1 day as long as all activities are completed within the allowable visit tolerance. For early terminations (ETs) that occur before the last visit in treatment period, see the activities listed for ET in this table. Visit 801 is only for study participants who are terminating early or not rolling into the long-term extension study (DRM06-AD07/J2T-DM-KGAA). 												
Visit number	1	2	3*	4	5*	6*	7*	8	9*	10	ET	V801*
Weeks from randomization	Screening (-4)	Baseline /Day 1	2	4	6	8	10	12	14	16	ET	Safety follow-up Week 26 (or approximately 12 weeks after last study drug injection)
Days from randomization	≤30	—	15	29	43	57	71	85	99	113	N/A	* = visit may be conducted remotely or on site, per preference of the study site or participant. See Section 4.1 for details about remote visits.
Visit interval tolerance (days)		—	±3	±3	±3	±3	±3	±3	±3	±3	N/A	±3
Informed consent	X											
Inclusion and exclusion criteria, review and confirm	X	X										
Demographics	X											
Preexisting conditions and medical history	X											
Prespecified medical history (indication and history of interest)	X											
Review of immunization record	X											Applies only to Tdap, MCV, BCG, or any live (attenuated) vaccine.

Notes:
 
 Visit 1 procedures may be conducted over more than 1 day as long as all activities are completed within the allowable visit tolerance. For early terminations (ETs) that occur before the last visit in treatment period, see the activities listed for ET in this table. Visit 801 is only for study participants who are terminating early or not rolling into the long-term extension study (DRM06-AD07/J2T-DM-KGAA). 													
Visit number	1	2	3*	4	5*	6*	7*	8	9*	10	ET	V801*	Comments
Weeks from randomization	Screening (-4)	Baseline /Day 1	2	4	6	8	10	12	14	16	ET	Safety follow-up Week 26 (or approximately 12 weeks after last study drug injection)	* = visit may be conducted remotely or on site, per preference of the study site or participant. See Section 4.1 for details about remote visits.

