Days from randomization	≤30	—	15	29	43	57	71	85	99	113	N/A	* = visit may be conducted remotely or on site, per preference of the study site or participant. See Section 4.1 for details about remote visits.
Visit interval tolerance (days)	—	—	±3	±3	±3	±3	±3	±3	±3	±3	N/A	±3
Eczema Area and Severity Index (EASI)	X	X		X				X		X	X	
Body Surface Area (BSA)	X	X		X				X		X	X	
Laboratory Tests and Sample Collections												
Hematology	X			X			X		X	X		
Clinical Chemistry	X			X			X		X	X		
Urinalysis	X			X			X		X	X		
Serum pregnancy	X											Only for women of childbearing potential (Section 8.2.3.1 and Appendix 10.4).
Urine pregnancy (local)		X		X		X		X	X			Only for women of childbearing potential (Section 8.2.3.1 and Appendix 10.4).
HIV screening tests	X											
Hepatitis C Virus (HCV) screening tests	X											HCV RNA will be measured to confirm positive hepatitis C virus antibody

Notes:												

 Visit 1 procedures may be conducted over more than 1 day as long as all activities are completed within the allowable visit tolerance. For early terminations (ETs) that occur before the last visit in treatment period, see the activities listed for ET in this table. Visit 801 is only for study participants who are terminating early or not rolling into the long-term extension study (DRM06-AD07/J2T-DM-KGAA). 												
Visit number	1	2	3*	4	5*	6*	7*	8	9*	10	ET	V801*
Weeks from randomization	Screening (-4)	Baseline /Day 1	2	4	6	8	10	12	14	16	ET	Safety follow-up Week 26 (or approximately 12 weeks after last study drug injection)
Days from randomization	≤30	—	15	29	43	57	71	85	99	113	N/A	* = visit may be conducted remotely or on site, per preference of the study site or participant.
Visit interval tolerance (days)		—	±3	±3	±3	±3	±3	±3	±3	±3	N/A	See Section 4.1 for details about remote visits.
												(Section 8.2.6).
Hepatitis B Virus (HBV) screening tests	X											Includes testing for HBsAg, anti-HBc, and anti-HBs.
HBV DNA	X							X				Only for participants who are anti-HBc reactive and anti-HBs nonreactive at screening (Section 8.2.5).
Total IgG	X											
Total IgA	X											
Anti-tetanus toxoid IgG antibody		X					X		X			At Week 12, collect this sample before the vaccine administration.
Meningococcal Group C serum bactericidal antibodies (human complement serum bactericidal assay)		X					X		X			At Week 12, collect this sample before the vaccine administration.

Notes:												

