4.1. Overall Design

Study KGAK is a Phase 3, 16-week, randomized, double-blind, placebo-controlled, parallel-group trial. The study will evaluate whether treatment with lebrikizumab compared with placebo affects seroresponses to non-live vaccines in patients with moderate-to-severe AD. In addition, the study will further assess the efficacy and safety of lebrikizumab compared with placebo in treating this patient population.

Study periods

KGAK has 3 study periods:

- Screening (Visit 1: ≥ 1 day)
- Treatment (Visits 2-10: 16 weeks)
- Safety follow-up (Visit 801: at Week 26 or approximately 12 weeks after last treatment)

See the Schedule of Activities (SoA) (Section 1.3) for additional details about the study periods and visit-specific assessments. A schematic of the study design is presented in Section 1.2.

Visit types

Depending on the preference of the study site or the study participant, some of the study visits may be performed either remotely or on site.

Remote visits may be conducted as follows:

- virtually (i.e., via telephone or telemedicine tools), *and*
- at a mobile location (e.g., a participant's home), if permitted by local laws and regulations.

See the table below for details about the visit types.

Study visit	Study week	Visit type
1	-4	On site only
2	Baseline	On site only
3	2	Remote or on site
4	4	On site only
5	6	Remote or on site
6	8	Remote or on site
7	10	Remote or on site
8	12	On site only
9	14	Remote or on site
10/early termination (ET)	16	On site only
801	Week 26 (or approximately 12 weeks after last treatment)	Remote or on site

Treatment groups

Participants found to be eligible according to all of the study entry criteria will be randomly assigned in a 1:1 ratio to receive either lebrikizumab or placebo (see Section 6.1 for dose and administration details).

Participants will be stratified at randomization according to their disease severity (i.e., IGA score of 3 vs 4). If the study is conducted in multiple countries, participants will also be stratified according to the geographical region.

Vaccine products

All participants will receive 2 vaccine injections at Week 12. For details, see Section 6.1.2.

Eligibility for long-term extension study

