4.4. End of Study Definition

A participant is considered to have completed the study if he or she has completed all required visits of the study, namely:

- Completed all required visits through Week 16 and through the safety follow-up period
- Completed all required visits through Week 16 and rolls into the LTE study (DRM06-AD07/J2T-DM-KGAA)

The “end of the study” is defined as the date of the last visit or the last scheduled procedure shown in the SoA for the last participant in the study globally.

5. Study Population

Prospective approval of protocol deviations *to recruitment and enrollment criteria, also known as protocol waivers or exemptions, is not permitted.*

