
then participants stay in the study to:
 
 • complete all the remaining study visits and assessments through Week 16 
AND
 
 • roll into the long-term extension study, if entry criteria are met 
OR
 
 • undergo the safety follow-up visit (V801). 	
then participants will not stay in the study and
 
 • undergo an ET visit 
AND
 
 • the safety follow-up visit (V801).

If the study drug is permanently discontinued before Week 12 and participants are continuing in the study, these study participants will not receive the vaccines at Week 12.

See the SoA for assessments to be performed at the time of the ET visit and safety follow-up. In addition to the SoA, safety follow-up is outlined in Section 8.2 (“Safety Assessments”) and Section 8.3 (“Adverse Events and Serious Adverse Events”) of the protocol.

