7.2. Participant Discontinuation/Withdrawal from the Study

A participant may withdraw from the study:

- at any time at his/her own request
- at the request of his/her designee (for example, legal guardian)
- at the discretion of the investigator for safety, behavioral, compliance, or administrative reasons
- if the participant becomes pregnant during the study (see Section 8.3.5 and Appendix 10.4, Section 10.4.3)
- if enrollment in any other clinical study involving an investigational product or enrollment in any other type of medical research judged not to be scientifically or medically compatible with this study
- if the participant, for any reason, requires treatment with another therapeutic agent that has been demonstrated to be effective for treatment of the study indication, discontinuation from the study occurs prior to introduction of the new agent

The participant must be discontinued from the study:

- if an investigator, site personnel performing assessments, or participant is unblinded

NOTE: In cases where there are ethical reasons to have the participant remain in the study, the investigator must obtain specific approval from the sponsor-designated medical monitor for the participant to continue in the study.

Discontinuation is expected to be uncommon.

At the time of discontinuing from the study, if possible, an ET visit should be conducted, as shown in the SoA. See SoA for data to be collected at the time of study discontinuation and follow-up and for any further evaluations that need to be completed. The participant will be permanently discontinued both from the study intervention and from the study at that time.

If the participant withdraws consent for disclosure of future information, the sponsor may retain and continue to use any data collected before such a withdrawal of consent. If a participant withdraws from the study, he/she may request destruction of any samples taken and not tested, and the investigator must document this in the site study records.

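### The schedule does not deliver the three-monthly HBV DNA repeat that Protocol 8.2.5 requires: no test is shown at early termination, and non-rollovers reach V801 98 days after the Week 12 test

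*Protocol*

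**What the plan says.** Protocol 8.2.5 admits participants who are anti-HBc positive with negative HBsAg and anti-HBs if their screening HBV DNA is negative, and attaches a condition: "Repeat testing for HBV DNA is required at least every 3 months during the study (Section 1.3". The same sentence gives the action on a positive result, which is to withhold or stop study drug.

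The Schedule of Activities (SoA, Protocol 1.3) is where that testing should appear. Its HBV DNA row carries the comment "Only for participants who are anti-HBc reactive and anti-HBs nonreactive at screening (Section 8.2.5" and two visible marks: screening and one on-study visit. The ET cell is blank.

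The study does not end at Week 16 for everyone. Protocol 4.1 lists as a study period "Safety follow-up (Visit 801: at Week 26 or approximately 12 weeks after last treatment", and one of the two routes to completion in 4.4 is "Completed all required visits through Week 16 and through the safety follow-up period". The SoA notes say who attends: "Visit 801 is only for study participants who are terminating early or not rolling into the long-term extension study". Under 7.1.2, participants who stop drug for reasons other than systemic rescue leave the study through an ET visit followed by V801. Those who stop for systemic rescue stay through Week 16.

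**The concern.** A safety requirement tied to enrolment should be traceable to a visit. Section 8 of the protocol makes adherence to the SoA mandatory, so a site that follows the table exactly can still breach 8.2.5. The people concerned were let in on a negative DNA result on the understanding that it would be repeated. Someone exposed to study drug who terminates before the single on-study test passes through ET without one.

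Two other provisions do not close the gap. Appendix 10.2 lets investigators add tests, but at their discretion. Abnormal liver tests can lead to hepatitis B testing under 8.2.7, but that depends on a chemistry draw, and the chemistry row shows no mark at V801.

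**Working it through.** **Inputs.** Interval: at least every 3 months (8.2.5); 3 × 365.25/12 = 91.3 days. Visit days, the ±3-day tolerance and screening up to 30 days before Day 1: SoA. Dosing at Day 1 and every 2 weeks through Week 14: 6.1.1. V801: Week 26, or about 12 weeks after the last injection.

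**Visit days.** Day = 7 × week + 1 reproduces the SoA: Week 12 = 85, Week 14 = 99, Week 16 = 113. Week 26 = Day 183, which is 12 weeks after the Week 14 dose.

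**Which visit carries the on-study mark.** Columns in the text copy of the table are displaced in places. Aligned with the EASI and BSA rows, the HBV DNA mark falls at Week 12. If the row is displaced like the anti-tetanus row, it falls at Week 14. Week 12 is more plausible because it is on site only, while Week 14 may be remote (4.1). The comment text occupies the V801 position, so a mark there can be neither confirmed nor excluded.

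**On treatment (Week 12 reading).** Day 1 to Week 12: 85 − 1 = 84 days (81 to 87). Week 12 to last dose: 99 − 85 = 14 days. Week 12 to Week 16: 28 days. Counted from Day 1, the rule is met.

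**Dosed at Week 14, not entering the extension.** Week 12 to Week 26: 183 − 85 = 98 days. With windows, 98 ± 6 = 92 to 104. Nominal excess: 98 − 91.3 = 6.7 days.

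**Terminating before Week 12.** V801 = last injection + 84 days:

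| Last dose | V801, days after Day 1 |
|---|---|
| Day 1 | 84 |
| Week 2 | 98 |
| Week 4 | 112 |
| Week 6 | 126 |
| Week 8 | 140 |
| Week 10 | 154 |

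Last doses at Weeks 2 to 10 give 98 to 154 days (3.2 to 5.1 months) with no test at ET. Even if V801 does carry a mark, that test comes late.

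**Not affected.** A participant dosed only on Day 1 reaches V801 at 84 days. One last dosed at Week 12 and tested there reaches V801 84 days later. Participants who stop for systemic rescue stay through Week 16 and so have the Week 12 visit.

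**Other column readings.** Mark at Week 14: Day 1 to test is 98 days (95 to 101) and test to V801 is 84 (78 to 90). Mark at Week 16: 112 and 70 days. Each reading has one interval above 91 days.

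**Starting point.** From the screening sample, Week 12 is 85 to 84 + 30 = 114 days away (117 with the window). 8.2.5 does not say which date starts the count.

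**Numbers of people.** The documents give no prevalence. Assuming 0.5% to 3% for this serology pattern:
- Monitored subset: 240 × 0.005 = 1.2 to 240 × 0.03 = 7.2.
- Early terminators, if all 240 − 218 = 22 planned losses were such: 22 × 0.005 = 0.11 to 22 × 0.03 = 0.66.
- Non-rollovers, assuming 10% to 50% of 218: 218 × 0.005 × 0.1 = 0.11 to 218 × 0.03 × 0.5 = 3.27.

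**The case against.** The strongest reply is that the rule is about dosing. Its stated action is to withhold or stop drug. On the Week 12 reading a test falls 84 days after Day 1 and the last dose follows 14 days later. Both gaps pass the limit after dosing has ended, when a positive result leads to referral rather than a dosing change. This stands as a limit on the consequence. It does not remove the conflict: 8.2.5 says during the study, and follow-up is a named study period. Nor does stopping injections end exposure at once. Protocol 8.4 asks for monitoring after an overdose until the drug is undetectable, at least 18 weeks, and V801 comes at about 12 weeks.

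A second reply is that 8.2.5 itself compels the test whatever the SoA shows. That is fair. The defect is a missing schedule mark, not a missing requirement.

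A reader might go further and infer that early terminators certainly have no repeat test at all. The documents do not support that, because the V801 cell cannot be read. What is visible is the blank at ET.

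A reader might also take the 22 participants between 240 and 218 as expected early terminations. Protocol 9.2 and 9.3 describe a loss of per-protocol evaluability, which also covers dosing noncompliance, prohibited treatment and visit-window deviations. The 0.11 to 0.66 above is therefore on the high side for a given prevalence.

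**Conclusion.** The conflict is real and minor. 8.2.5 sets a three-month maximum during the study, and the row it cites cannot deliver it with one on-study test, whichever column that test sits in. The clearer shortfall is in participants who terminate before Week 12 after a last dose at Weeks 2 to 10. The non-rollover excess is about a week, and at the most favourable corner of the windows (92 days) it nearly vanishes.

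The size rests on the Week 12 reading, on counting from Day 1, and on an assumed prevalence under which well under one affected early terminator is expected. The documents do not support a claim that on-treatment HBV monitoring lapses on that reading and count. The co-primary vaccine-response analysis is not affected.

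**What to change.** For the subset named in the SoA comment:

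- Confirm that the existing on-study mark is at Week 12.
- Add a conditional mark at ET.
- Add a conditional mark at Week 16 for those not entering the extension. Completers have no ET visit, so ET and V801 marks alone would leave non-rollovers at 98 days. Participants who roll over do not need it.
- Confirm or add a mark at V801.
- State in 8.2.5 whether the three months run from the screening sample or from randomization. If from screening, an earlier on-study test is also needed, because Week 12 can be 114 days away.

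Counted from Day 1, the intervals become: Day 1 to Week 12, 84 days (81 to 87); Week 12 to Week 16, 28 (22 to 34); Week 16 to Week 26, 70 (64 to 76). For an ET visit by Week 12, Day 1 to ET is at most 87 days. ET to V801 is at most 84 (87 with the window), since ET is on or after the last injection.

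The cost is one amendment and a few assays. On the assumptions above, Week 16 + ET + V801 gives 0.11 + 0.11 + 0.22 = 0.44 at the low end and 3.27 + 0.66 + 3.93 = 7.86 at the high end. The samples can share the PK and ADA draws; the ET draw should be checked, because those rows have the same column uncertainty. V801 may be remote and need a mobile draw. ET is not guaranteed either: "At the time of discontinuing from the study, if possible, an ET visit should be conducted, as shown in the SoA". Someone who skips it would have only the V801 test.
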